X Test can be done according to the opinion of the treating physician

X Puncture site should be warm and well perfusedp.

X Chest x-ray is recommended if clinically indicated e.g. to answer the question if the disease is stable

X Re-check inclusion criteria 1

X (since last visit): Healthy / Sick-better / Sick-same / Sick-worse / Patient died

X Pulmonary exacerbation is defined as sustained worsening of the patient's condition from stable state and beyond normal day to day variations. The exacerbation is rated as indicated belowo.

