h Health economics assessment with the use of a special questionnaire which has to be filled out by the parents or adult patients.

i Quality of Life assessment with the use of the questionnaire PedsQL for different age groups which has to be filled out by parents and/or patients

j For Electrocardiography (ECG), ophthalmological review and Echocardiography (Echo) please see Chapter 5. If a routine ophthalmological examination was done within 3 month before Visit 1, no additional ophthalmological exam is required.

k Pregnancy test only has to be performed in girls of childbearing age and only if sexual relations are known or probable. It is at the discretion and responsibility of the attending physician to decide, whether a pregnancy test is necessary or not. The pregnancy test can be performed in the urine or serum.

l The following parameter will also be assessed, if there is **oxygen demand**:

1. O2 via nasal cannula or via face mask: O2-Flow (l/min)
2. on high-flow nasal cannula: Flow air (l/min), O2-Flow (l/min), FiO2

m The following parameter will also be assessed on ventilation: ventilation method, duration of ventilation (hours/day/only for non-invasive ventilation), PEEP (cmH2O), PIP (cmH2O), FiO2, Ti (sec), MPAW (cmH2O) and Oxygenation Index (OI);  
In addition, if patients on the heart lung machine (e.g. NO (%), ECLS (VV/VA/ECLA), Flow/time since insertion) will be documented descriptively.

n Calculation of Oxygenation Index (OI): OI = (FiO2 \* MPAW)/PaO2

with MPAW = ((frequency \* inspiration time)/60) \* ((inspiratory pressure (PIP) – PEEP) + PEEP)); If PaO2 is not available, PcapO2 can be used.)

o Start date, End date, Patient returned to baseline function? Y/N

1. Increase in respiratory rate? Y/N/not done.

2. Increase or development of dyspnea ? Y/N

3. Newly developing or increased abnormalities on chest imaging ? Y/N/not done

4. Onset/increase of oxygen demand to attain the individual baseline saturation ? Y/N

5. Need for an additional level of ventilatory support (in addition to oxygen) ? Y/N

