## 8 STATISTICS

Details of the statistical analysis of the data collected in this trial will be documented in a Statistical Analysis Plan (SAP) that will be generated by IZKS Mainz and finalized before closing the data base and prior to breaking the blind. The SAP is based on the protocol including all amendments. The document may modify the plans outlined in this protocol; however any major modifications of the primary outcome definition and/or its analysis will also be reflected in a protocol amendment. Any deviation from the original statistical plan must be described and justified in the final report. The statistical analysis will be conducted by means of SAS®.

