1.2 Study Design

[figure not shown]
[figure not shown]
This study is an explorative, prospective, randomized, double-blind, placebo controlled investigation of hydroxychloroquine (HCQ) in pediatric ILD. The treatments are organized in START and STOP blocks, which can be initiated in sequence, as needed by the subjects. Each patient can participate in each block, but only once in each block.

In the START block subjects are randomized to parallel-groups, then the placebo group is switched to active drug.

In the STOP block, subjects on HCQ are randomized into parallel-groups treated with placebo or HCQ to investigate the withdrawal of HCQ for assessment of its efficacy.

It is planned to assess >100 subjects for eligibility and to allocate 80 subjects. An equal distribution between START and STOP blocks is expected.

Study flow chart

Trial schedule START HCQ Block

Visit	Screening evaluations and Visit 1	Visit 2	No Visit	Visit 3	No Visit	Visit 4
Action	„Start of baseline“	“End of baseline“ + Day 1 of treatment	Every 7 days at home + web/tele feed-back	End of 1 st Tx period	Every 7 days at home + web/tele feed-back	“End of trial“
Trial day	-28 to -3	1		28 (-4, +7)		56 (-4, +7)
Demographics (e.g. sex, age, race)	X					
Patient information, informed consent	X					
Previous and concomitant diseases	X	X		X		X
Previous and concomitant treatments	X	X		X		X
Inclusion/exclusion criteria	X					
Pregnancy test ^k	X			X		X
Randomization ^l	X					
Physical examination	X	X		X		X
Vital signs (BP, pulse, temp, cardiotoxicity, hypoglycaemia)	X	X		X		X
ECG	X*			X		X
Ophthalmologic review ^m	X*					
Lab ⁿ (GOT/GPT/Crea/BUN/CK/GGT/LDH/BB/DIFF drug level /save EDTA, blood glucose)	X*			X		X
pO ₂ , pCO ₂ (capillary)	X	X***		X***		X***
Primary outcome ^e O ₂ -sat. in room air	X	X	-	X	-	X
Secondary outcomes						
Respiratory rate, in room air	X	X	X	X	X	X
Retractions	X	X	X	X	X	X
Coughing	X	X	X	X	X	X
Oxygen demand	X	X	X	X	X	X
Chest x-ray scoring for child	X*			X****		
Pulmonary hypertension (Echo)	X*					
Quality-of-life ⁱ	X*					X
Health Economics ^h	X*					X
Weight for height ^b	X*					X
Adverse events		X	X	X	X	X
Additionally in children > 5 years						
FEV1 % predicted (recorded in L) ^d	X	X		X		X
FVC % predicted (recorded in L) ^d	X	X		X		X
6 minute walking distance (meter) ^g	X	X		X		X
O ₂ -saturation before and after 6MWT	X	X		X		X
Borg scale ^j	X	X		X		X
Additionally in ventilated patients						
Oxygenation index (OI)	X	X	X	X	X	X

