Duration (h) of mechanical ventilation	X	X	X	X	X	X
NO (%), ECLS (VV/VVA/ECLA/Flow/time since insertion)	X	X	X	X	X	X

X* Tests must be done before first drug dosing

X** Test can be done according to the opinion of the treating physician

X*** Test can be done facultative, but should be done, if initial pCO₂ has been elevated

X**** Chest x-ray is recommended if clinically indicated e.g. to answer the question if the disease is stable

Trial schedule STOP HCQ Block

Visit	Visit 1 + Screening	Visit 2	No Visit	Visit 3	No Visit	Visit 4	No Visit	Visit 5	Visit 6
Action	„Begin of baseline“	“End of baseline“ + Day 1 of withdrawal treatment	2 weeks of withdrawal, at home + web/tele feed-back	4 weeks of withdrawal treatment	6 weeks of withdrawal, at home + web/tele feed-back	8 weeks of withdrawal treatment	10 weeks of withdrawal, at home + web/tele feed-back	“End of trial” after 12 weeks of withdrawal treatment	Follow up after 12 weeks of open observation
Trial day	-30 to -10	1 (-1, +8)	14 (-7, +7)	28 (-7, +7)	42 (-7, +7)	56 (-7, +7)	70 (-7, +7)	84 (-7, +7)	168 (-7, +7)
Demographics (e.g. sex, age, race)	X								
Patient information, informed consent	X								
Previous and concomitant diseases	X	X		X		X		X	X
Previous and concomitant treatments	X	X		X		X		X	X
Inclusion/exclusion criteria	X								
Pregnancy test ^k	X			X		X		X	
Randomization ^a	X								
Physical examination	X	X		X		X		X	X
Vital signs (BP, pulse, temp, cardiotoxicity, hypoglycaemia)	X	X		X		X		X	X
ECG	X*			X		X		X	
Ophthalmologic review ^j	X*								
Lab ^c (GOT/GPT/Crea/BUN/CK/GGT/LDH/ BB/DIFF, blood glucose, drug level (EDTA blood)	X*			X		X		X	X (only EDTA for drug level)
pO ₂ , pCO ₂ (capillary)	X	X**		X**		X**		X**	X***
Primary outcome ^e									
O ₂ -sat, in room air	X	X	-	X	-	X	-	X	X
Secondary outcomes									
Respiratory rate, in room air	X	X	X	X	X	X	X	X	X
Retractions	X	X	X	X	X	X	X	X	X
Coughing	X	X	X	X	X	X	X	X	X
Oxygen demand	X	X	X	X	X	X	X	X	X
Chest x-ray scoring for child	X*								X***
Pulmonary hypertension (Echo)	X*								
Quality-of-life ⁱ	X*							X	X
Health Economics ^h	X*							X	X
Weight for height ^b	X*							X	X
Adverse events	X	X	X	X	X	X	X	X	X
Additionally in children > 5 years									
FEV1 predicted (recorded in L) ^d	X	X		X		X		X	X
FVC predicted (recorded in L) ^d	X	X		X		X		X	X
6 minute walking distance (meter) ^g	X	X						X	X
O ₂ -saturation before and after 6MWT ^g	X	X						X	X
Borg scale ^f	X	X						X	X
Additionally in ventilated patients									

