Oxygenation index (OI)	X	X	X	X	X	X	X	X	X
Duration (h) of mechanical ventilation	X	X	X	X	X	X	X	X	X
NO (%) ^g , ECCL (VVVA/ECCL)Flow/time since insertion	X	X	X	X	X	X	X	X	X

X* Tests must be done before first drug dosing

X** Test can be done facultative, but should be done, if initial pCO₂ has been elevated

X*** Chest x-ray is recommended if clinically indicated e.g. to answer the question if the disease is stable

a Randomization must occur after all inclusion and exclusion criteria are met directly after consent to the study is given and at least 1 week before first dose of HCQ or withdrawal treatment. This is necessary to allow for preparation and shipping of the study medication.

c Blood sample should include: Blood count with differential, GOT, GPT, gGT, Creatinine, LDH, BUN, Creatine kinase, drug level, 3 ml EDTA-blood

d Spirometry will be performed pre-bronchodilator in children age ≥ 5 years. SOP will be provided.

e Measurement of O₂-Saturation, respiratory rate and O₂ flow (if necessary) in awake patient at rest:

If not on O₂: after 5 min at rest, room air, then measure twice over 1 min. each, at least 1 min. apart

If on O₂:

- BEFORE withdrawal (after 5 min at rest with steady state O₂ supplement, then measure over 1 minute)
 - Then withdraw O₂ to obtain steady state O₂-Sat. in room air (at least 30 seconds without change). Then measure twice over 1 min. each, at least 1 min. apart. If falls below SpO₂<80% place back in oxygen and note as <80%.

f Borg-Scale: assessment of dyspnea (0 – 10: 0 = no dyspnea at all, 5 = severe dyspnea, 10 = extremely severe dyspnea)

g Standard exercise testing (6-minute-walk test): SOP will be provided

h Health economics assessment with the use of a special questionnaire which has to be filled out by the parents

i Quality of Life assessment with the use of the questionnaire PedsQL for different age groups

j For ophthalmological review please see Chapter 5.1

k Pregnancy test only has to be performed in girls of childbearing age and only if sexual relations are known or probable. It is at the discretion and responsibility of the attending physician to decide, whether a pregnancy test is necessary or not.

2 Analysis Populations

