4.2 Primary Variable

START HCQ block and STOP HCQ block

The primary variable is the response rate measured by the oxygen saturation in room air.

START HCQ block

Relative change from trial day 1, i.e. Visit 2, through day 28, i.e. Visit 3, change from active compound compared to change from placebo

STOP HCQ block

Relative change from trial day 1, i.e. Visit 2, through day 84, i.e. Visit 5: change from active compound compared to change from placebo

A) Non-ventilated patients in room air or on O2-supplement

Oxygen saturation in room air

Assessment:

1) If not on O2:

(after 5 min at rest room air, then measure twice over 1 minute each, at least 1 min apart)

** O2 Sat (mean value)*

* Respiratory rate (mean value)

2) If on O2: BEFORE withdrawal:

(after 5 min at rest with steady state O2 supplement, then measured over 1 minute)

* O2 Flow

* O2 Sat (mean value)

* Respiratory rate

Then withdraw O2:

Steady state O2 Sat in air obtained. Steady state minimum SpO2 should be at least 30 seconds without change. Then measured twice over 1 minute each, at least 1 min apart.

If falls to SpO2<80% place back in oxygen and note as <80%.

* O2 Sat (mean value)

* Respiratory rate (mean value)

B) If on high-flow nasal prongs:

O2-flow and air-flow

C) Ventilated patients:

Oxygenation index (OI)

OI = (FiO2 * MPAW) / PaO2

with

FiO2 = Fraction of inspired oxygen

MPAW = Mean airway pressure (= ((frequency * inspiration time)/60) * ((inspiratory pressure (PIP) – PEEP) + PEEP)))

PaO2 = Partial pressure of oxygen in arterial blood

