6.7.1 Efficacy

For both, START and STOP HCQ blocks absolute and relative change under the active compound from trial day 1, i.e. Visit 2, to START block: day 28, day 56 STOP block: day 84 each, will be compared between treatment groups .

The following variables will be investigated:

- Oxygen saturation (O2-sat, in room air) (only absolute, as relative already primary outcome)
- Respiratory rate (RR, in room air) (relative and absolute)
- Retractions (yes/no)
- Coughing last 24 h (yes/no)
- Oxygen requirement (yes/no)
- pO2, pCO2 (capillary, in room air)
- Chest x-ray scoring for chILD
- Overall survival (time from randomization until death; if no death observed, time will be censored at time point of last (follow-up-)visit): a Kaplan-Meier plot will be provided; if possible, the median overall survival and corresponding 95%-confidence interval will be calculated
- Cumulative amounts of steroid equivalents per time period
- If > 5 y old
 - FEV1 % predicted (recorded in L)

- FVC % predicted (recorded in L)
- reference values according to the GLI 2012 lung function regression equations
- 6 minutes walking distance (meter)
- O2-saturation before and after 6MWT
- If ventilated:
 - Duration (h) of mechanical ventilation
 - NO (%), ECMO yes/no, if yes VA/VV, double lumen vs. single lumen, Flow-rate.

Additionally, FEV₁, FVC, FVC predicted, 6 min walking distance will be displayed by Box-Plots and All-in-one plots over each time point.

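### The SAP schedules make the capillary blood gas optional at visits where the protocol schedules it, which leaves the footing of the exploratory pO2/pCO2 comparison unclear (minor)

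*SAP*

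**What the plan says.** **SAP 1.2, START schedule.** Capillary pO2/pCO2 has a plain mark at screening. At Visits 2, 3 and 4 it has a triple-asterisk mark, explained as "Test can be done facultative, but should be done, if initial pCO₂ has been elevated".

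**SAP 1.2, STOP schedule.** The row is plain at screening. Visits 2 to 5 carry a double asterisk with the same explanation. Visit 6 carries a triple asterisk, which in this legend means "Chest x-ray is recommended if clinically indicated e.g. to answer the question if the disease is stable".

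**Protocol Tables 1-1 and 1-2.** The same sample is scheduled at START Visits 1 to 4 and STOP Visits 1 to 8. After Visit 1 the only note on it concerns technique: "Puncture site should be warm and well perfused".

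**Analysis.** SAP 6.7.1 lists "pO2, pCO2 (capillary, in room air") among the secondary variables. It compares absolute and relative change from Visit 2 to days 28 and 56 (START) or day 84 (STOP). SAP 5.1 plans no substitution of missing values.

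**Oxygenation index.** Both SAP schedules give ventilated patients a separate row, "Oxygenation index (OI"), with a plain mark at every visit. SAP 4.2 defines its oxygen term as "PaO2 = Partial pressure of oxygen in arterial blood". The protocol's footnote to its schedule tables adds a fallback, "If PaO 2 is not available, PcapO 2 can be used", which the SAP does not repeat.

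**Relation of the documents.** Protocol section 8 states: "The SAP is based on the protocol including all amendments".

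**The concern.** A change from Visit 2 needs a gas at Visit 2 and another at the endpoint visit. Under the SAP's own schedule both are optional, and the only trigger that makes them advisable is a raised initial pCO2. The children with paired values would then be those who were hypercapnic at entry, plus those whom the site chose to sample. The choice at Visits 3 to 5 comes after randomisation and may depend on how the child is doing. SAP 6.7.1 names no fallback baseline and no adjustment for the initial value.

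A narrower problem concerns ventilated children. The SAP defines the oxygenation index on arterial blood only. Neither document schedules an arterial sample; the protocol lets one replace the capillary sample when it is available. A ventilated child without an arterial line would rely on the protocol's capillary fallback, and so on a sample that another row of the SAP calls optional.

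**Working it through.** The documents give no power or precision figure for this endpoint, so there is nothing to reproduce. The check sets the schedules side by side and then gives an illustration of scale.

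**Step 1: the schedules**

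| Visit | SAP gas row | Protocol gas row | Needed in SAP 6.7.1 for |
|---|---|---|---|
| Visit 1, both blocks | Required | Required | Not used |
| START Visit 2 | Facultative | Scheduled | Baseline |
| START Visits 3 and 4 | Facultative | Scheduled | Days 28 and 56 |
| STOP Visit 2 | Facultative | Scheduled | Baseline |
| STOP Visits 3 and 4 | Facultative | Scheduled | Not used |
| STOP Visit 5 | Facultative | Scheduled | Day 84 |
| STOP day 168 (SAP Visit 6, protocol Visit 8) | Chest x-ray marker | Scheduled | Not used |

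Every gas value that SAP 6.7.1 uses is optional in the SAP and scheduled in the protocol. The only value required in both is Visit 1, which SAP 6.7.1 does not use. The STOP Visit 6 marker looks like a carry-over from the START legend, where the triple asterisk does mean facultative. It does not affect the comparison, which ends at day 84.

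**Step 2: the oxygenation index.** Its row is unconditional at Visit 2 and at Visits 3 (START) and 5 (STOP), so the schedule does not waive it. The gap is in the source of the oxygen value: arterial only in the SAP, arterial or capillary in the protocol.

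**Step 3: scale, under assumptions.** Planned size: 80 patients / 2 blocks / 2 arms = 20 per arm. Assume unit SD at each visit and a correlation of 0.7 between visits. The share with raised initial pCO2 is not given; take 20% to 50%, and suppose only those children are sampled.

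- SD of a change: √(2 × (1 − 0.7)) = 0.775.
- Standard error of the difference between arms: 0.775 × √(2/n).
- n = 20: 0.24 SD. n = 10: 0.35. n = 6: 0.45. n = 4: 0.55.
- Simulation, where the number sampled varies by chance, gives 0.24, 0.36, 0.49 and 0.57.

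In terms of detectable effect, with two-sided 5% and 80% power assumed, (1.96 + 0.84) × √(2/n) gives 0.89 SD at n = 20, 1.02 at 15, 1.25 at 10 and 1.77 at 5. Here the SD is that of the quantity compared.

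**Step 4: bias and adjustment.** With a true effect of −0.50 SD, 30% raised, and the rest sampled with probability 0.8 if their value is worse and 0.2 otherwise, one simulation gives an estimate of −0.57 SD with standard error 0.37. Other versions of discretionary sampling gave −0.49 to −0.50. The shift therefore depends on the sampling rule assumed and is small beside the standard error.

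Adjusting for the initial value gives a residual SD of √(1 − 0.7²) = 0.714. The standard error with full sampling is then 0.714 × √(2/20) = 0.23, against 0.24. In the −0.57 scenario, adjustment moves the estimate to −0.53.

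**The case against.** The strongest reply is that sites collect data under the protocol, which schedules the gas at all these visits. The SAP's schedule looks like a copy that does not match the current protocol in other respects either: its STOP block ends at Visit 6 rather than Visit 8, and its quality-of-life and ECG visits differ. The analysis section itself contains no facultative rule, and the endpoint is secondary and explicitly exploratory. SAP section 6 already reports the number of observations by treatment group, so a thin comparison would be visible. SAP 6.6 speaks in the past tense of too few patients in both blocks, so it was written with enrolment known, and rewording a legend then cannot create samples.

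Most of this stands. It removes any claim that the comparison must rest on a selected subset. It does not settle which rule applied to every child. Recruitment began in Q4 2015, the current protocol cites a source dated January 2017, and its section 4.1.10 still speaks of Visit 6 in the STOP block as if it closed the trial. Some children may have been followed under a schedule like the SAP's. That is an inference, not something the documents show.

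Two stronger readings are tempting, and neither should be adopted.

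- A reader might infer that the primary outcome becomes optional for ventilated children. The documents do not support this: the facultative note is on the capillary gas row, and the oxygenation index row is unconditional. The index also concerns a minority, since protocol 8.3.1 expects most children to be in room air or on supplemental oxygen.
- A reader might conclude, because the endpoint is defined in room air while the schedule rows say only capillary, that pO2 should be compared only where both samples were taken in room air. A shorter row label does not contradict the definition. That restriction would also condition on respiratory support after randomisation, which is a selection of the same kind.

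**Conclusion.** The mismatch is real and minor. The SAP marks as optional every capillary gas that its pO2/pCO2 comparison uses, the protocol schedules all of them, and the STOP Visit 6 marker points to the wrong note. If some children were sampled under the SAP rule, the consequence is lost precision and selection by baseline pCO2 and site discretion in one exploratory secondary comparison. The documents do not show whether this happened.

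The figures are illustrative only. They rest on an assumed correlation of 0.7, an assumed 20% to 50% with raised pCO2, and no sampling of the others. That last assumption is the extreme reading of an optional test.

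For the primary outcome, what remains is a definitional gap: the SAP omits the capillary fallback for the oxygenation index. It affects only ventilated children without an arterial sample.

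**What to change.** 1. In SAP 1.2, reconcile the pO2/pCO2 rows of both schedules with protocol Tables 1-1 and 1-2, and correct the STOP Visit 6 marker. If some patients were followed under a facultative rule, say so and say which.
2. In SAP 6.7.1, compare pO2 and pCO2 between arms adjusted for the initial (Visit 1) value, which both documents require. Use Visit 1 as the baseline where Visit 2 is missing, and report how many children this applies to in each arm.
3. In SAP 4.2, carry over the protocol's capillary fallback for the oxygenation index, and state that the index uses a gas from the same visit.

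The cost is SAP wording and a few programming lines. No new procedure is needed, because the protocol already schedules the samples. The drawback is a baseline taken from two visits for some children, which adjustment for the Visit 1 value partly handles. Adjustment reduces selection on the initial value; it does not remove selection that depends on later course.

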## STOP HCQ block

Table 1-2

Visit	Visit 1 + Screening	Visit 2	Email- /Phone- Visit	Visit 3	Email-/ Phone- Visit	Visit 4	Email-/ Phone- Visit	Visit 5	Email-/ Phone- Visit	Visit 6	Email- /Phone- Visit	Visit 7	Email- /Phone- Visit	Visit 8
Action	„Begin of baseline“	“End of baseline“ + Day 1 of withdrawal treatment	2 weeks of withdrawal, at home	4 weeks of withdrawal treatment	6 weeks of withdrawal, at home	8 weeks of withdrawal treatment	10 weeks of withdrawal, at home	“End of trial“ after 12 weeks of withdrawal treatment	2 weeks of open observation at home	Follow up after 4 weeks of open observation	6 weeks of withdrawal, at home	Follow up after 8 weeks of open observation	10 weeks of withdrawal, at home	Follow up after 12 weeks of open observation
Trial day	-30 to -10	1	14 (-7, +7)	28 (-7, +7)	42 (-7, +7)	56 (-7, +7)	70 (-7, +7)	84 (-7, +7)	98 (-7, +7)	112 (-7, +7)	126 (-7, +7)	140 (-7, +7)	154 (-7, +7)	168 (-7, +7)
Demographics (e.g. sex, age)	X													
Patient information, informed consent	X													
Previous (last 12 months) and concomitant diseases	X	X	X	X	X	X	X	X	X	X	X	X	X	X
Previous (last 3 months) and concomitant treatments	X	X	X	X	X	X	X	X	X	X	X	X	X	X
Inclusion/exclusion criteria	X	X 												
Pregnancy test k	X*			X		X		X						
Randomization a	X													
Trial medication supply to patient		X		X		X								
History (cardiotoxicity, hypoglycaemia)	X	X		X		X		X		X		X		X
Physical examination	X	X		X		X		X		X		X		X
Vital signs (BP, pulse, temp) b	X	X		X		X		X		X		X		X
ECG j	X*							X						X
Ophthalmologic review l	X*													X 
Lab c (GOT/GPT/Crea/Potassium/CK/gGT/LDH/BB/DIF F / HCQ drug level, blood glucose)	X*			X		X		X		X (only HCQ drug level)		X (only HCQ drug level)		X (only HCQ drug level)
pO 2 , pCO 2 (capillary)	X	X 		X 		X 		X 		X 		X 		X 
O 2 -sat e , in room air	X	X	X	X	X	X	X	X	X	X	X	X	X	X
Respiratory rate, in room air	X	X	X	X	X	X	X	X	X	X	X	X	X	X

CONFIDENTIAL

Visit	Visit 1 + Screening	Visit 2	Email- /Phone- Visit	Visit 3	Email-/ Phone- Visit	Visit 4	Email-/ Phone- Visit	Visit 5	Email-/ Phone- Visit	Visit 6	Email- /Phone- Visit	Visit 7	Email- /Phone- Visit	Visit 8
Retractions	X	X	X	X	X	X	X	X	X	X	X	X	X	X
Coughing	X	X	X	X	X	X	X	X	X	X	X	X	X	X
Oxygen demand c	X	X	X	X	X	X	X	X	X	X	X	X	X	X

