#### 4.1.10 Not permitted medication

Each previous and concomitant medication has to be documented in detail.

**Systemetic steroids:** pulsed glucocorticoids in the 4 weeks before entry into the study (day 1) and throughout the trail (V4 in START block and V6 in STOP block) are not allowed. A continous daily or alternate day oral dose of glucocorticoids is allowed and has to be stable in the 4 weeks before entry into the study (day 1) and throughout the trail.

Not permitted medication	Comedications very carefully to be considered (further explanation in the text)
Hepatotoxic medications, also caution with alcohol	Antiepileptics
Inhibitors of the monoaminooxidase	Digoxin
Arrhythmogenic medications	Cyclosporine
Amiodarone	Methotrexate
Moxifloxacin	Corticosteroids
Halofantrin	Aminoglycosides
Metronidazole	Agalsidase-beta
Phenylbutazon	Iaronidase
Probenecid	Neostigmine, Pyridostigmine
Indomethacin	Antacids
Penicillamin	Caolin
Pyrimethamine/Sulfadoxine	Cimetidine
Other medications that decrease the convulsive threshold	Praziquantel
Bupropion	Rabies vaccination with HDCV
Mefloquine	Insulin, antidiabetics
Other antimalarial	Ampicillin
	Azathioprin
	Other disease-modifying antirheumatic drugs

Due to an increased risk of ventricular arrhythmias the use of arrhythmogenic medication, as for example amiodarone or moxifloxacin, is not permitted during the trial. Halofantrin can prolong the QT interval with increased risk of arrhythmias and is therefore not permitted during the trial.

It is prohibited to use other hepatotoxic medication or inhibitors of the monoaminooxidase during the trial. Adolescent patients should be explained that no larger quantity of alcohol should be consumed during the treatment with HCQ.

The use of medication, that lowers the convulsive threshold, as for example mefloquine and bupropion, is not allowed during the trial, as there is an increased risk for seizures. The effect of antiepileptics can be reduced by hydroxychloroquine.

The use of digoxin and cyclosporine is not prohibited during the trial, but investigators must be aware that hydroxychloroquine may increase the plasma concentrations of digoxin and cyclosporine. So in this case a strict control of plasma-drug-level is necessary to avoid intoxication with digoxin or cyclosporine.

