4.2.1 Efficacy

The following variables will be investigated:

- Oxygen saturation (O2-sat, in room air) (only absolute, as relative already primary outcome) assessed at every visit (not web/tele feedback)
- Respiratory rate (RR, in room air) (relative and absolute) assessed at every visit and every web/tele feedback
- Retractions (yes/no) assessed at every visit and every web/tele feedback
- Coughing last 24 h (yes/no) assessed at every visit and every web/tele feedback
- Oxygen requirement assessed at every visit and every web/tele feedback
- pO2, pCO2 (capillary, in room air)
- Chest x-ray scoring for chILD assessed at screening and visit 3 (START HCQ Block) and visit 5 (STOP HCQ Block)
- Overall survival
- If > 5y old
 - FEV1 % predicted (recorded in L)
 - FVC % predicted (recorded in L)
 - reference values according to the GLI 2012 lung function regression equations
 - 6 minutes walking distance (meter)
 - O2-saturation before and after 6MWT
 - Borg scale
- If ventilated:
 - Duration (h) of mechanical ventilation
 - NO (%), ECMO yes/no, if yes VA/VV, double lumen vs. single lumen, Flow-rate.

4.2.2 *Safety/Tolerability*

Adverse events, clinical laboratory values (GOT, Creatinine, gGT, blood count, differential, LDH, BNP, steady state drug level), ECG, ophthalmologic review

Adverse events will be documented during the study at each visit (exemption: START HCQ between Visits 1 and 2. However, occurring AEs between those visits are not treatment emergent).

Laboratory data will be assessed at screening, visit 3 and visit 4 in the START HCQ Block and at screening, visit 3, 4 and visit 5 and EDTA additionally at visit 6 in the STOP HCQ Block.

Vital signs (respiratory rate, height, weight, BMI, heart rate, blood pressure (systolic and diastolic), temperature, hypoglycaemia (yes/no), appropriate observation of blood glucose levels (yes/no), cardiotoxicity (yes/no), appropriate ECG (yes/no)) will be assessed at screening, and every following visit (not web/tele feedback).

A physical examination will be done at the same visits.

Symptoms and clinical course of treatment will be documented at the same time points as the physical examination is performed and at telephone contact visit.

4.2.3 *Quality of Life (Peds QL)*

Not applicable.

4.2.4 *Health Economics*

Not applicable.

5 Treatment of Missing Values and Outliers

5.1 *Missing Values*

No substitution of missing values is planned.

5.2 *Outliers*

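### The SAP's visit schedule does not match the protocol: STOP Visit 6 means day 168 in one and day 112 in the other, and the SAP does not specify the day-28 START quality-of-life comparison

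*SAP*

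**What the plan says.** **STOP follow-up.** The SAP schedule in section 1.2 goes from Visit 5 (day 84) straight to Visit 6 at day 168, "Follow up after 12 weeks of open observation". Protocol Table 1-2 has three on-site visits in the same period: Visit 6 at day 112, "Follow up after 4 weeks of open observation", Visit 7 at day 140 and Visit 8 at day 168. At each of them the laboratory row reads "X (only HCQ drug level". SAP 4.2.2 repeats its own numbering in the text and plans "EDTA additionally at visit 6 in the STOP HCQ Block". It names no later sample.

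**START quality of life.** In the SAP's START schedule the row "Quality-of-life" is marked at screening and at Visit 4 (day 56). Protocol Table 1-1 marks it at screening, Visit 3 (day 28) and Visit 4. Protocol 3.4 lists quality of life among the outcomes compared between active and placebo from day 1 to day 28. SAP 6.7.1 names days 28 and 56 for START but leaves quality of life off its variable list. SAP 6.7.3 plans t-tests on values and on changes from baseline without naming a visit. SAP 4.2.3 marks quality of life as not applicable.

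**Relation between the documents.** Protocol section 8 states: "The SAP is based on the protocol including all amendments".

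**The concern.** A visit number is often what a programmer uses to select and label records. Here one number stands for two different days, and the SAP has no entry for STOP Visits 7 and 8. The follow-up drug levels serve a stated STOP secondary objective (blood levels before and after treatment), and SAP 6.7.2.2 plans summaries of laboratory measures over time. A table built from the SAP's visit numbers could show day-112 levels under a day-168 heading and leave out the samples from days 140 and 168.

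For START quality of life, day 28 is the only post-baseline time at which HCQ is compared with placebo. The SAP schedule is the only place in the SAP that gives timing for this outcome, and it omits that visit. An analyst working from the SAP alone could report only day 56, or could choose the visit after seeing the data.

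**Working it through.** **Inputs.** End of blinded STOP treatment: day 84 (both documents). Follow-up labels: 4, 8 and 12 weeks of open observation, windows of 7 days either side (protocol Table 1-2); 12 weeks only (SAP 1.2). The START placebo arm begins HCQ four weeks after the active arm (protocol 1.4). HCQ half-life: 30 to 60 days, with a slow elimination phase of 18 days also given (protocol 1.3).

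**Step 1. Reproduce each document's Visit 6.**
- SAP: 84 + 12 × 7 = 168. This agrees with its stated day.
- Protocol: 84 + 4 × 7 = 112. This agrees with its stated day.
- Protocol Visit 7: 84 + 8 × 7 = 140. Visit 8: 84 + 12 × 7 = 168.

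Each schedule is internally consistent. The SAP's Visit 6 corresponds to the protocol's Visit 8.

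**Step 2. Size of the label shift.** 168 − 112 = 56 days. The windows are 105 to 119 and 161 to 175, so they do not overlap, and a visit cannot be in window for both.

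**Step 3. What 56 days means for a drug level.** Assume first-order decline and no HCQ taken during open observation. The fractional fall is 1 − 2^(−56/h) and the ratio of levels is 2^(56/h).

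| Half-life h (days) | Fall from day 112 to day 168 | Ratio of levels |
|---|---|---|
| 60 | 48% | 1.9 |
| 30 | 73% | 3.7 |
| 18 | 88% | 8.6 |

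The content of a Visit 6 drug-level table therefore depends heavily on which numbering is used.

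**Step 4. START exposure at the two quality-of-life times (nominal days).**
- Day 28: 28 days of HCQ in the active arm, 0 in the placebo arm.
- Day 56: 56 days in the active arm, 56 − 28 = 28 in the arm that switched.

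Day 28 compares HCQ with placebo. Day 56 compares 56 with 28 days of HCQ.

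**Step 5. What is not affected.** START Visits 2 to 4 and STOP Visits 2 to 5 fall on the same nominal days in both documents. The primary time points, START day 28 and STOP day 84, agree. For STOP quality of life, both schedules include Visit 5 (day 84).

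**Step 6. Smaller mismatches.** The SAP schedule lists BUN, and SAP 4.2.2 lists "blood count, differential, LDH, BNP, steady state drug level", where the protocol's schedule and section 3.4 list potassium. Protocol 4.1.10 gives the end of the steroid restriction as "V4 in START block and V6 in STOP block" and also says it holds throughout the trial. In Table 1-2, V6 is day 112 and the last visit is V8.

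**The case against.** The case for leaving the SAP as it is has four parts.

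1. **The SAP may depart from the protocol.** Section 8 goes on to allow the SAP to modify the plan, and it asks for a protocol amendment only for major changes to the primary outcome or its analysis. This stands: a different secondary schedule is not in itself a breach. It does not help here, because the SAP nowhere presents the difference as a deliberate change.

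2. **Nothing excludes day 28.** SAP 6.7.3 restricts its tests to no visit, and the protocol collects PedsQL at day 28. A reader might infer that the placebo-controlled comparison will be lost. The documents do not go that far; they leave it unspecified. The day-56 comparison is also legitimate in its own right, because 56 against 28 days of HCQ is a stated START secondary objective.

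3. **Efficacy is keyed to trial days.** SAP 6.7.1 uses days 28, 56 and 84 and plans no contrast at a STOP follow-up visit. A reader might infer that STOP follow-up efficacy results would land on the wrong day, but no such contrast is planned. The exposure is the drug-level sampling point and any descriptive follow-up summary, and mislabelling requires programming by visit number without checking dates.

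4. **The laboratory mismatch has little consequence.** SAP 6.7.2.2 covers each laboratory measure, so potassium that is collected would still be reported. This stands; it is a matter of alignment only.

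A reader might also infer that the SAP was written from a superseded schedule. The V6 end point in protocol 4.1.10 matches the SAP's numbering and makes this plausible, but neither document shows version dates that would establish it.

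**Conclusion.** The mismatch is real and should be corrected, but its reach is limited. STOP Visit 6 differs by 56 days between the documents, and two of the protocol's three follow-up drug-level visits have no place in the SAP. On the protocol's half-lives, and assuming first-order decline with no HCQ taken, levels at the two days would differ 1.9- to 8.6-fold. For START quality of life, the only post-baseline time in the SAP falls after the placebo arm has switched, and SAP 4.2.3 and 6.7.3 disagree on whether the outcome is analysed at all. The day-28 comparison is therefore unspecified and may be omitted; it is not ruled out.

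The documents do not support reading this as a threat to the primary endpoint. The primary days agree, and all analyses are described as exploratory.

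**What to change.** In the SAP:
- Replace the schedules in section 1.2 with protocol Tables 1-1 and 1-2.
- In 4.2.2, key the STOP follow-up drug levels to trial days 112, 140 and 168 instead of to a visit number.
- In 6.7.3, state that the between-arm PedsQL comparison is at day 28 in START and day 84 in STOP, and that START day 56 is reported as 56 against 28 days of HCQ.
- Remove the contradiction between 4.2.3 and 6.7.3.
- Align the laboratory list (BUN, BNP) with the protocol's (potassium).

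Separately, the V6 end point in protocol 4.1.10 must be reconciled with Table 1-2 and with that section's statement that the restriction lasts throughout the trial. Which is intended is for the sponsor to state.

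The cost is an SAP text update and a protocol clarification. No new data are needed, because the protocol already schedules these assessments. The update should be made before unblinding, so that the quality-of-life visit is not chosen after the results are known. If the blind has already been broken, the change should be described and justified in the final report, as protocol section 8 requires of deviations.
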